Purpose of the Study

Aim 1: Examine the feasibility and acceptability of a national, low-cost, community-based, peer-led, weight loss program (Take Off Pounds Sensibly, TOPS) for overweight and obese African American breast cancer survivors in the local chapter of a national African American breast cancer support group (Sisters Network Triangle North Carolina, SNTNC).

Hypothesis 1: The TOPS format, materials, and content will be feasible and acceptable to overweight and obese African American breast cancer survivors in SNTNC.

Aim 2: Assess the weight change of overweight and obese African American breast cancer survivors after 6 months in the TOPS program to gather data for sample size calculations for a future RCT.

Hypothesis 2: Overweight and obese African American breast cancer survivors in TOPS will lose 5% of their initial body weight, which is clinically significant, within 6 months.

Background & Significance

Mounting evidence links overweight and obesity to cancer. In women diagnosed with breast cancer, obesity contributes to both breast cancer-specific and cardiovascular disease mortality. In one study, breast cancer survivors diagnosed at ≥66 years were more likely to die from cardiovascular disease than breast cancer. Therefore, obesity also plays a role in their cardiovascular mortality. Unfortunately, breast cancer treatment can exacerbate these issues because it may be associated with weight gain; increased cardiovascular events; and decreased physical function.

Compared to the general population, African American women have higher rates of overweight and obesity among those with and without breast cancer; gain more weight after they are diagnosed with breast cancer; and have worse outcomes for breast cancer mortality and cardiovascular disease. For women diagnosed with breast cancer, interventions targeting diet, weight loss, and physical activity have been associated with clinically significant weight loss; decreased mortality; reduced risk of breast cancer recurrence; and fewer cardiovascular events. Unfortunately, African American women lose less weight than other groups in standard weight loss programs.

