In one randomized controlled trial, African American breast cancer survivors in an expert-led intervention – weekly didactic sessions, twice weekly supervised exercise sessions, and twice weekly text messages with community-based nutritionists and exercise trainers – lost an average of 3.6% of their weight and 44% of participants lost at least 5% of their initial weight. However, personnel increase the intervention costs, and there is no infrastructure for nationwide dissemination of this program. To decrease adverse clinical and mortality outcomes among African American breast cancer survivors, a weight management intervention with scalable infrastructure that can be implemented in low-resource settings is needed.

A national, low-cost, community-based, peer-led weight loss program (Take Off Pounds Sensibly, TOPS) can fill this unmet need. TOPS is a nonprofit, evidence-based weight loss program with a national infrastructure that offers a pragmatic option to help women diagnosed with breast cancer manage their weight. First, it includes all of the components that the NIH asserts should be included in "safe and effective" weight loss programs. Second, [name] retrospective analyses showed: 1) TOPS participants lose a clinically significant amount of weight and maintain the loss for up to 7 years. Third, its peer-led, community-based structure ensures each chapter is contextually tailored for its members. For instance, in a successful pilot study, [name] started three TOPS chapters specifically for older African American women; and one chapter continued for almost 8 years after the study ended in 2012 (until the COVID-19 pandemic). Fourth, TOPS costs participants less than \$100 per year. Finally, TOPS's nationwide infrastructure, with chapters in every state, can facilitate dissemination and implementation. However, because women with breast cancer have greater psychosocial stressors, including time-consuming treatment regimens and fear of recurrence, they may need different levels of support than those offered in standard TOPS chapters, and this study can reveal those elements and provide preliminary data for a future randomized controlled trial (RCT).

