Sisters Network Triangle North Carolina (SNTNC) is an affiliate chapter of Sisters Network, Inc., a national African American breast cancer survivorship organization. SNTNC was established in 2003. Prior to the COVID-19 pandemic, SNTNC held separate monthly meetings in both Raleigh and Durham, NC. Since the pandemic, SNTNC combined the Raleigh and Durham meetings into one monthly virtual Zoom meeting. In the past, SNTNC has participated in research projects about survivorship, barriers to care, and treatment adherence.

For African American women diagnosed with breast cancer, our long-term goals are to decrease cancer-specific, cardiovascular, and all-cause mortality. The objective of this proposal is to conduct formative research to determine if the format and materials of the TOPS program are feasible and acceptable to overweight and obese African American breast cancer survivors. This project seeks to address the health disparities of overweight and obesity and cardiovascular disease among African American breast cancer survivors and benefits from the following: 1) the existing infrastructure of the SNTNC, the Raleigh/Durham chapter of a national African American breast cancer survivorship organization; 2) the successful weight loss of participants in the TOPS program; and 3) [name] experience with studies of the TOPS program. The outcomes will be a) determination of the feasibility and acceptability of the TOPS program by women of SNTNC; b) recommendations the women of SNTNC have to modify the program to make it relevant to their experiences; and c) preliminary weight change data for sample size calculations for a future RCT of TOPS for weight change among this population.

This work will develop the evidence base for a scalable weight loss intervention among African American breast cancer survivors – a population with poor breast cancer and cardiovascular outcomes. If effective, these results have the potential to help increase both the survival and quality of life for this population.

Design & Procedures

Research design. Part of the study design will be the further development of study documents including TOPS programs, survey questions, and focus group scripts. The documents will not be used until full IRB approval is granted for the final drafts via amendments.

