This project will be a six-month single arm study that will use qualitative and quantitative methods to measure the feasibility and acceptability of the TOPS program among African American breast cancer survivors. Qualitative methods will collect data about participants' perceptions of the program and suggestions for modification to make it relevant to them and their experiences. We will conduct up to five focus groups and up to 10 in-depth interviews. Quantitative methods will measure recruitment, retention, and weight change.

Subjects. Overweight and obese African American breast cancer survivors in the Sisters Network Triangle North Carolina (SNTNC).

Inclusion criteria:

18 years old and over

Women diagnosed with breast cancer

BMI ≥ 25 kg/m2 after completion of primary therapy (surgery, radiation, adjuvant or neo-adjuvant chemotherapy)

Regular access to a computer and internet

Exclusion criteria:

Under 18 years old

Have not had a breast cancer diagnosis

Currently undergoing infusion chemo therapy treatment

Do not have access to a computer and the internet

BMI is less than 25 kg/m2

Women whose oncology providers do not agree with their participation in a weight loss program Participating in another weight loss program

If on insulin or sulfonylureas and provider does not agree to help manage their medications. They will need a signed provider permission form.

Study Setting. The study will be conducted via Zoom. Since the COVID-19 pandemic, SNTNC has met online. Approximately 50 to 60 women participate each month. Thus, the group is used to meeting in the virtual space. Duration. Subjects will join newly formed TOPS chapters for 6 months. Then, they will be asked to participate in focus groups to collect data about their perceptions of the TOPS program.

Recruitment and Screening. The study will enroll up to 50 women, who will be recruited through the Sisters Network Triangle North Carolina (SNTNC). [name], MSN, RN, is a Patient Navigator at the Duke Cancer Center. She is also the co-founder, past president, and current program manager for SNTNC and she is an enthusiastic proponent of this project. She will assist with the recruiting efforts.

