Participants that attend the Zoom information session and are interested in participating in the study will be sent a link to our REDCap project. They will be able to review information about the study such as why we are doing the study, risks/benefits, and determine if they would like to continue by answering some questions. They will provide some information to identify themselves and to determine eligibility. Once eligible, participants will be able to review the e-consent. They can have as much time as needed to review, ask the study team questions via phone or email, and sign using an e-signature. After they sign they will be sent a copy of the e-consent via email that they provide. If they are ineligible, they will not be able to continue on to the e-consent.

Intervention. Participants will be invited to join new chapters of the TOPS weight loss program created for the study. Each participant will be offered a free one-year membership in the TOPS program. Participants will receive the "TOPS Plus" new member packet—one-year membership in a local TOPS chapter; My Day One: A Ready-Set-Go Guide for Healthy Living is a 24-page booklet of weight loss basics with a six-week lesson plan; a one year subscription to TOPS News, a bimonthly magazine published exclusively for TOPS members; Real Life: The Hands-on, Pounds-off Guide is a 304-page weight management lifestyle guide; Food Exchange Cards; TheraBands® Resistance Bands; My Real Progress, a 12-week food and fitness journal. TOPS Usual Procedures. The TOPS program usually consists of weekly private weigh-ins on the chapter scale, where the weight recorder notes each person's weight on their individual Weight Chart. Then, there is a group meeting, where members receive educational information on topics such as healthy eating, exercise, or behavior modification. Participants usually get a "provider-approved" weight goal. Modified COVID-19 Procedures. Because of social distancing requirements due to the pandemic, we will have to modify the usual procedures. The study will provide each participant with a scale, and members will provide the weight recorder with their weights each

week. The weight recorder will still record each person's weight on their individual Weight Chart. We will also set an initial weight loss goal of 5% of initial weight, which is considered clinically significant.

Additional Opportunity:

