There is an additional opportunity for some participants to become a TOPS leader. This weight loss program requires peer leadership, which means one member of each group will be the leader. This involves reading the materials ahead of time and taking a training on TOPS leadership. Participants will receive an additional compensation for each training module completed to become a TOPS leaders.

Data collection. Focus groups and interviews. All individuals who enroll in the study will be invited to participate in 6 month focus groups and interviews, even if they did not remain in the program. Groups will be led by an experienced moderator and last for 60-90 minutes using open-ended questions to elicit the most information. Focus groups will have up to 6 participants and will be conducted via Zoom by the Behavioral Health and Survey Research (BHSR) Core, led by [name], MPH. We will conduct up to 10 individual interviews with those who are unable to participate in the focus groups. The interviews will include the same themes as the focus groups. Evidence suggests that data saturation can occur within 12 interactions, with primary themes arising as early as six. In this way, we will be able to discover factors associated with program continuation and withdrawal. Focus groups and interviews will be taped and transcribed. Both [name]'s and [name]'s previous experiences with SNTNC have established these as acceptable forms of assessment with this group. All interviews will be audio recorded (via Zoom) and transcribed. All of the patient information will be stored in a secure, shared Duke drive that only the study personnel will have access to. The focus groups will be recorded and stored securely on Duke's Zoom platform, participants will be provided with a password to enter the virtual meeting. Audio will be shared to Duke Box. Notes about the interview, transcripts, and audio will be stored in Duke Box and stored in study records for at least six years after the study is done. After six years, we will destroy the records, or we will remove all information identifying participants.

Survey: All individuals who enroll in the study will be invited to complete a brief survey about their experience at the 6 month interval.

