Focus group and interview guide development. Focus group and interview guides will be developed using the Framework for Reporting Adaptations and Modifications – Enhanced (FRAME), which is typically used to retrospectively document modifications that occurred during implementation. In this case, we will use FRAME to guide questions for prospective adaptations for our population of interest. Instead of asking, "What is the nature of content modifications?" we will offer options for possible modifications, such as removing, substituting, or adding elements. Focus groups and interviews will inform the adaptation and implementation of the TOPS program for African American breast cancer survivors. Weight change. Weight change will be calculated at 3 and 6 months as percentage change from initial weight. If the pandemic restrictions allow and participants are comfortable, we can consider study visits for data collection. However, we plan to provide participants with smart scales to transmit data to a secure application.

Risk/Benefit Assessment

There is minimal risk to the subjects. Weight loss has been shown to be safe in obese, older individuals. Additionally, this study will recruit participants into Take Off Pounds Sensibly (TOPS), a nationally available, community-based, peer-led weight loss program. The TOPS program is being used in non-medical settings throughout the United States and Canada and poses minimal risk to participants. Individuals must have a body mass index of 25 or greater to participate in the current study. The minimal risk to human subjects for participation in this study is greatly outweighed by potential health benefits that may accrue participants and by the importance of the scientific knowledge that may reasonable be expected to result from this work.

Data Analysis & Statistical Considerations

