Focus groups. We will import all transcripts into the Nvivo software to facilitate organization and analysis. We will use a 5-stage approach to conduct thematic analysis (familiarization; identifying a thematic framework; indexing; charting, and interpretation). Experienced qualitative researchers from the BHSR core will work with the study team to conduct the analysis. Familiarization will involve the entire research team reviewing 2-3 transcripts to identify initial coding themes to become familiar with the data. Identified themes will be used as the initial coding framework to conduct line by line coding of a single transcript. The team will meet to discuss the transcript and modify the initial framework. Next, two researchers will code the remaining transcripts. Coding will include memos for each transcript to annotated coders questions, decision about the data, and reflections on analysis. Each coder will also create an overview memo to collect observations that cut across transcripts during the coding process. After coding, the team will meet to discuss themes, sort codes, and restructure the initial framework as similarities and differences are identified. In the final stage, the team will identify major themes and associated quotes to summarize the results. We will also conduct member checking where we will ask providers and patients interviewed to provide feedback on the summarized data.

Weight change. Weight change will be calculated as last observation carried forward and completers' analyses. For both analyses, weight change will be calculated as difference between baseline weight at 3 and 6 months and as a percentage of initial weight. Weight change will also be categorized in the following groups: weight loss 0 to <5%; weight loss ≥5%; and weight gain.

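### Completers' weight change is a risky basis for sizing the future RCT if women who lose less leave more; plan from all enrolled women and obtain leavers' 6-month weights

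*Protocol*

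**What the plan says.** The Weight change paragraph under Data Analysis & Statistical Considerations reads: "Weight change will be calculated as last observation carried forward and completers"' analyses. Both are applied at 3 and 6 months, as a difference from baseline and as a percentage of initial weight. They have equal standing, and the protocol names no third method.

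The purpose of the estimate is stated twice. Aim 2 is "to gather data for sample size calculations for a future RCT", and the outcomes listed in Background & Significance include "preliminary weight change data for sample size calculations for a future RCT of TOPS". The protocol does not say which of the two figures will be carried to that calculation.

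Three other places bear on what could be done:
- Intervention, Modified COVID-19 Procedures: women receive a scale, and "members will provide the weight recorder with their weights each" week.
- Data collection: every enrolled woman is invited to the 6-month focus groups and interviews, "even if they did not remain in the program", and to a 6-month survey.
- Design & Procedures, Weight change: "we plan to provide participants with smart scales to transmit data to a secure application".

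On dropout, Research design says only that "Quantitative methods will measure recruitment, retention, and weight change". No dropout rate or SD of weight change is given. The one numerical benchmark is an expert-led trial whose participants "lost an average of 3.6% of their weight", with 44% losing at least 5%.

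**The concern.** A sample size for a comparison of means depends on (SD/mean effect)². In a weight-loss programme, women who see little loss may well be the ones who stop coming. The women left at 6 months are then a favourable selection: their mean loss is too high and their spread somewhat too narrow. Both errors reduce the calculated N, so they add up.

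LOCF behaves differently. It freezes a leaver at the partial loss reached when she left. If she would have stayed on course, LOCF understates both the mean and the SD, and the two errors largely cancel in the ratio. If she regains, LOCF overstates her loss.

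At stake is an underpowered RCT. The completers' figure is the more flattering of the two under loss-dependent dropout, and nothing in the protocol steers planners away from it. A leaver's 6-month weight that is not obtained at the time cannot be recovered later.

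**Working it through.** **Nothing to reproduce.** The protocol gives no sample-size calculation, SD, alpha, power or dropout rate, so what follows is an illustration.

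**Inputs.** From the protocol: mean loss 3.6% (benchmark trial), weekly weights, enrolment of up to 50. Assumed: SD of true 6-month loss 6 points, weekly noise 1 point, linear courses over 26 weeks, leavers staying on course, zero change in RCT controls, and dropout depending on the last recorded loss. Total SD at 6 months is √(6² + 1²) = 6.08.

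Three settings for dropout and its link to loss were simulated. Women one SD above and below the mean differ by 12 points, so their weekly odds of leaving differ by (1/0.95)^12 = 1.9, (1/0.90)^12 = 3.5 and (1/0.82)^12 = 11.

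**Formulas.** Share of needed N: R = (SD/mean)² estimated ÷ (SD/mean)² true, with the true value (6.08/3.60)² = 2.852. Power when 80% is intended: Φ(2.80·√R − 1.96).

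| | Weak | Middle | Strong |
|---|---|---|---|
| Dropout | 10% | 20% | 30% |
| Odds of leaving per point lost | ×0.95 | ×0.90 | ×0.82 |
| Completers, mean (SD) | 3.69 (6.07) | 3.99 (6.02) | 4.71 (5.74) |
| Completers, (SD/mean)² | 2.706 | 2.276 | 1.485 |
| Completers, share of N | 95% | 80% | 52% |
| Power obtained | 78% | 71% | 52% |
| LOCF, mean (SD) | 3.44 (5.92) | 3.31 (5.75) | 3.26 (5.56) |
| LOCF, share of N | 104% | 106% | 102% |

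With no link, completers give 3.6% and 100% of N.

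**Other inputs, by formula.** Suppose a woman stays when a latent normal variable, correlated ρ with her loss, exceeds its d-quantile c (d = dropout). Let λ = φ(c)/(1 − d). The completers' mean is μ + ρ·SD·λ and their variance is SD²·[1 − ρ²λ(λ − c)]. For μ = 5, SD = 6, d = 0.30, ρ = 0.5: c = −0.524, λ = 0.497, mean 6.49, SD 5.61, R = (5.61/6.49)² ÷ (6/5)² = 0.52. Over μ of 3.6 or 5, SD 4 to 6, d 10% to 40% and ρ 0.1 to 0.7, R runs from 0.97 to 0.23. Under this selection model, LOCF simulated with linear loss and uniform exit times gives 0.74 to 1.29 against continued courses, and 0.55 to 1.27 if leavers return to baseline.

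**The SD the benchmark implies.** If weight change is normal with mean 3.6 and 44% at or above 5, then SD = (5 − 3.6)/0.151 = 9.3. In the same three settings, completers then give about 88%, 59% and 28% of N, and LOCF about 100%, 93% and 74% to 76% (the last varies between simulation runs).

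**If leavers regain 0.66 points a month (assumed, SD 6).** The truth becomes 3.24 (SD 6.04), 2.91 (6.02) and 2.66 (5.99). Completers give 78%, 53% and 29% of N; LOCF 85%, 70% and 57%. A mixed model with random intercept and slope, fitted to 400 simulated studies of 50 women per setting, gives 82%, 68% and 56%. Without regain the same model gives 100%, 100% and 99%, but it is correctly specified there because the simulated courses are linear. Setting leavers back to baseline (or to their last weight if that was above baseline) gives means of 3.25, 3.01 and 2.93, closer to the regain truth than any of the three methods.

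**Value of leavers' weights.** In the strong setting without regain, if 50% or 80% of leavers give a 6-month weight, the completers' share rises from 52% to 76% or about 90%. In the middle setting it rises from 80% to 90% or 96%.

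**The case against.** The strongest counter-argument is that the protocol plans two analyses, and the deficit belongs to only one of them. A reader might infer from the completers' figures that the RCT will be sized on completers; no section says so. LOCF sits beside it, is near adequate at SD 6 without regain, and a gap such as 4.7% against 3.3% in the strong setting would itself be a warning. This stands, and it limits the point to a risk. The warning does not, however, tell the planner which figure to use, and at the SD the benchmark implies LOCF can fall short too.

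Second, a mixed model does not clearly beat LOCF. With regain, LOCF is slightly closer at SD 6 in all three settings. This stands as well. It is why the model needs a return-to-baseline sensitivity analysis, and why leavers' actual weights matter more than the choice of model.

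Third, sampling error is large. With 50 women and SD 6 the 95% CI half-width is 2.01 × 6/√50 = 1.71, so an interval of 1.89 to 5.31 alone moves N between (3.6/5.31)² = 46% and (3.6/1.89)² = 363% of the truth. The weak-link bias (0.1 points) is trivial beside that; the strong-link bias (1.1) is smaller than the half-width but not negligible, and the completers' interval does not reveal it.

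Fourth, an SAP, not shown here, may name a planning estimate and further analyses. Their absence from the protocol is therefore not the complaint. The complaint is that the methods the protocol does name are not well suited to the stated purpose, given the data it plans to collect.

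**Conclusion.** The point holds as a conditional risk and a low-cost improvement. If dropout depends on loss, completers overstate the mean, understate the SD and lead to too small an RCT. The illustrative size is 95% to 52% of the needed N, resting on mean 3.6%, SD 6, dropout 10% to 30%, an assumed link, no regain and zero control change; the wider grid gives 97% to 23%. None of these inputs except the 3.6% is in the protocol, so a reader should not take 52%, or any single figure, as an established shortfall. If leaving is unrelated to loss and leavers do not regain, completers are unbiased.

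Nor do the documents support reading both named methods as plainly invalid. LOCF is about right at SD 6 without regain, through offsetting errors; it has no fixed direction of error, and it is optimistic when leavers regain, as is the mixed model.

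**What to change.** 1. At the 6-month contact already planned with all enrolled women, or through the smart scales, obtain a current weight from women who left, and use it in the analysis.
2. In the Weight change paragraph of Data Analysis & Statistical Considerations, state that the mean, SD and 95% CI carried to RCT planning come from all enrolled women, using a likelihood-based mixed model on the weekly weights. Add one sensitivity analysis in which women without a 6-month weight return to baseline, or keep their last weight if it was above baseline.
3. Keep LOCF and completers as descriptive displays, and state that the RCT will not be sized on completers alone.

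Cost: one extra item at the 6-month contact, transfer of the weekly weights from the chapters' charts to the study data, a few lines of text and slightly more analysis. The headline loss may look less favourable. The gain is mainly over completers and is small over LOCF at SD 6.

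### Minor: the weight-change groups put exactly zero change under weight loss, because the small-loss group starts at 0 and there is no no-change group

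*Protocol*

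**What the plan says.** All references are to the protocol; no SAP was available.

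- **Data Analysis & Statistical Considerations, Weight change:** "Weight change will be calculated as last observation carried forward and completers' analyses". In both, change is taken at 3 and 6 months, as a difference and as a percentage of initial weight. It is then also grouped as "weight loss 0 to <5%; weight loss ≥5%; and weight gain".
- **Purpose of the Study, Hypothesis 2:** participants "will lose 5% of their initial body weight" within 6 months. This is the threshold behind the ≥5% group.
- **Design & Procedures, Recruitment and Screening:** "The study will enroll up to 50 women".
- **Design & Procedures, Modified COVID-19 Procedures:** weights are reported weekly ("members will provide the weight recorder with their weights each" week). The later Weight change paragraph adds that "we plan to provide participants with smart scales to transmit data to a secure application".
- **Design & Procedures, Research design:** "Quantitative methods will measure recruitment, retention, and weight change".

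The protocol has no group for unchanged weight. It does not give the scale resolution, and it does not say whether LOCF uses the baseline weight when a woman has no later one.

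**The concern.** The small-loss group includes its lower bound of 0. Zero is neither a gain nor a loss of 5% or more, so it has only one place to go, and that place is labelled weight loss. Women who did not lose weight are then reported among those who did.

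The misplacement runs one way: it can add women to a loss group and never remove one. It applies at 3 and 6 months and in both analyses. A reader who adds the two loss groups to obtain the share that lost weight gets a figure that is too high whenever anyone is unchanged.

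Under LOCF there may be a second source of zeros. If baseline counts as an observation that can be carried forward, a woman who never supplies a later weight has a change of exactly 0% and enters the small-loss group, although nothing is known about her weight. The protocol leaves this open, so this part is conditional.

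This is not a detail left to an SAP. The protocol itself fixes the cut-points and labels, and an SAP that followed them would repeat the fault.

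**Working it through.** The plan gives no figure to reproduce here. The check has three parts.

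**1. Where each value falls.** Let L be the percentage loss, 100 × (baseline − follow-up) / baseline. As written, the groups are 0 ≤ L < 5, L ≥ 5 and L < 0.

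| L (%) | Group as written |
|---|---|
| −3 | gain |
| −0.1 | gain |
| 0 | loss, 0 to under 5 |
| 0.1 | loss, 0 to under 5 |
| 4.99 | loss, 0 to under 5 |
| 5 | loss, 5 or more |
| 8 | loss, 5 or more |

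On a grid from −30% to +30% in steps of 0.01, every value falls in exactly one group. The scheme is exhaustive and mutually exclusive. The only fault is that L = 0 carries a weight-loss label.

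**2. How many measured zeros to expect.**

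Input from the protocol: at most 50 women.

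Assumptions, none of them in the protocol:
- L is normally distributed with mean μ = 0, 3 or 5% and SD σ = 4 or 6%.
- Baseline weight W is 90 kg, with a range of 70, 90 and 110 kg.
- The reading unit u is 0.1 kg, 0.2 lb (0.0907 kg) or 1 lb (0.4536 kg).

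A zero is recorded when the change is smaller than half a reading unit. With h = 100 × u / (2W),

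P(zero) = Φ((h − μ)/σ) − Φ((−h − μ)/σ).

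Worked case with W = 90 kg and u = 0.1 kg: h = 100 × 0.1 / 180 = 0.0556%.
- μ = 0, σ = 4 gives P = 1.11%, the largest value; 50 × 0.0111 = 0.55 women.
- μ = 5, σ = 4 gives P = 0.51%, the smallest value; 50 × 0.0051 = 0.25 women.

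| Reading unit | P(zero), 90 kg | Women of 50, 90 kg | P(zero), 70–110 kg | Women of 50, 70–110 kg |
|---|---|---|---|---|
| 0.1 kg | 0.51–1.11% | 0.25–0.55 | 0.42–1.42% | 0.21–0.71 |
| 0.2 lb | 0.46–1.01% | 0.23–0.50 | 0.38–1.29% | 0.19–0.65 |
| 1 lb | 2.30–5.02% | 1.15–2.51 | 1.88–6.46% | 0.94–3.23 |

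These counts are for one time point. Treating baseline and follow-up as both rounded to the unit gives the same probabilities to within 0.01 percentage points.

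The chance that at least one of 50 women is affected, over 70 to 110 kg, is 1 − (1 − P)^50:
- 0.1 kg: 1 − (1 − 0.0042)^50 = 19% to 1 − (1 − 0.0142)^50 = 51%.
- 1 lb: 1 − (1 − 0.0188)^50 = 61% to 1 − (1 − 0.0646)^50 = 96%.

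**3. Women with no later weight, only if baseline is carried forward.** For such a woman L = 100 × (W0 − W0)/W0 = 0. Each adds 1/50 = 2.0 percentage points to the small-loss group. The protocol gives no expected number. For illustration, if 10%, 20% or 30% of 50 women had no later weight, 5, 10 or 15 women would enter that group. If baseline is not carried forward, only the measured zeros in part 2 are affected.

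**Effect on the other results.** Moving L = 0 elsewhere changes the ≥5% group by 0 points. The mean change does not use the groups, so it does not move either.

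**The case against.** The case for leaving the text alone has four parts.

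- **The rule is clear.** Every value has one place, and the label shows that its range starts at 0, so two analysts would build the same table. This is true, and it is why the fault is one of boundary and label and not of ambiguity. It does not make unchanged weight a loss. If the group was meant to hold stable women, its label is wrong; if it was meant to hold only losers, its bound is wrong. Either way the sentence needs an edit.
- **Nothing important depends on it.** The grouping is secondary to the continuous change, Hypothesis 2 uses 5%, and no endpoint of any weight loss is defined. This stands in full. The favourable bias shows only in the small-loss row and in any total a reader forms from the two loss rows.
- **The size is assumed and mostly below one woman.** This also stands for readings to 0.1 kg or 0.2 lb. The larger counts need readings to 1 lb, which the protocol neither states nor rules out.
- **The LOCF route is hypothetical.** The handling of women with only a baseline weight is commonly left to an SAP. Weekly reports and smart scales make such women less likely, and retention is measured separately. For these reasons that route is kept conditional, and the finding does not rest on it.

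**Conclusion.** The point holds and is minor. As written, unchanged weight is reported as weight loss at both time points and in both analyses, and the error can only flatter the programme.

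Its expected size is under one woman of 50 per time point for fine readings, and about one to three for readings to 1 lb. These figures rest on the assumed baseline weights, mean, SD and reading unit, and on full enrolment. The addition under LOCF depends on a rule the protocol does not state. The fault is confined to one descriptive table; neither the 5% threshold result nor the data for planning the later RCT is touched.

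**What to change.** Redefine the three groups as loss of 5% or more, loss above 0 and below 5%, and no change or gain. A separate no-change group would serve equally well. If the present counts are preferred, relabelling the small-loss group as no change or loss below 5% also removes the error.

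If LOCF is to carry baseline forward, show the number of women with no post-baseline weight on its own line so that they are not read as having lost weight. Both planned analyses can stay as they are.

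The cost is a change to one sentence, with no extra data, participants or analyses. With the new lower bound, the small-loss share becomes slightly less favourable.
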